6.3 Subject Population for Analysis

The population whose data will be subjected to the study analysis will include all subjects enrolled in this study that completed the Cytosponge administration and have pathology results available from the subsequent routine care endoscopy with biopsy.

7 Safety and Adverse Events

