4.4 Early Withdrawal of Subjects

Subjects will be considered to have completed the study after completion of the last study visit (follow-up phone call). Subjects may be withdrawn prior to this for any of the following reasons:

- Death, or
- Lost to Follow-Up, or

- Withdrawal of consent, or
- Discontinuation by the investigator.

Documentation must be maintained at the site for any subject withdrawals. Subjects unable to complete Cytosponge administration will be withdrawn from the study (discontinued by investigator). Three attempts at contact using two different methods are required prior to determination that the subject is lost to follow-up. Attempts at contact must be with certified letters OR documented telephone contact. If a subject is withdrawn prior to completion of the study, the site should complete and submit a change of status case report form. See section 8.3 for additional information on case report forms. Subjects who withdraw after completion of the initial Cytosponge administration will not be replaced. Withdrawn subjects will not be followed, unless they have an active adverse event (AE) at the time of withdrawal. Subjects withdrawn while experiencing an adverse event will be followed until resolution of the AE.

5 Study Procedures

Assessment	Screening/Enrollment Visit	Follow-Up Phone Call (7 days +/- 2 days after Enrollment)	Follow-Up Cytosponge Administration ¹	Follow-Up Phone Call (7 days +/- 2 days after each follow-up Cytosponge)
Informed Consent Form	X			
Demographics	X			
Medical History	X			
Inclusion/Exclusion Criteria	X			
Cytosponge Administration	X		X	
Routine Care Endoscopy with Biopsy	X ²		X ²	
Visual Scale	X ³	X	X ³	X
Impact of Events Scale		X		X
Procedure Preference and Acceptability Questionnaire		X		X
Adverse Events⁴	X	X	X	X

¹ After enrollment, if subjects receive treatment for their EoE and return to the enrolling site for an upper endoscopy as part of their standard of care, then subjects will be asked to repeat the Cytosponge procedure prior to each follow-up standard of care endoscopy.

²Routine care biopsies should be taken during the endoscopy following the Cytosponge as this is considered standard of care for the target population. No research-specific biopsies will be obtained during the procedure.

³ The VAS should be administered immediately following completion of the Cytosponge and prior to the upper endoscopy.

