5.1.3 Cytosponge Administration

The Cytosponge™ device (referred to hereafter as the "Cytosponge") will be supplied by Covidien GI Solutions to the participating sites. Study sites will be responsible for storage and accountability of the device. The Cytosponge lifetime/use by date will be confirmed on the product packaging. The device received FDA 510(k) clearance on November 26, 2014 (K142695). The Cytosponge device consists of a spherical 3.0 cm diameter reticulated polyester foam compressed and encapsulated in a standard vegetarian capsule (size 00).

Subjects will undergo administration of the Cytosponge™ according to the IFU. Briefly, subjects will be placed in the seated position and will swallow the capsule with 150 – 250 mL of water. Additional water may be used if necessary. The sponge is attached to a length of suture material which passes out through the capsule. The suture is affixed to a retainer card which is held by the subject or administrator to prevent inadvertent swallowing of the suture. The string is to be held without tension as peristalsis and gravity advance the capsule into the stomach.

The capsule dissolves in the stomach, allowing the sponge to expand to its full size. Seven minutes and 30 seconds to ten minutes after ingestion, the sponge is then withdrawn by gentle traction on the suture, collecting cells from the lining of the esophagus in passing.

After retrieval, the string is cut and the retrieved foam sphere containing the cytological specimen is immersed in fixative and stored refrigerated (1° to 12°C [34° to 54°F]) until shipped. Samples will be shipped in batches to the Mayo Clinic for initial processing, then batch shipped to the [name] lab in Cambridge for additional analysis. On arrival at the lab, the fixative is spun in a centrifuge, and the pelleted cells are embedded in paraffin using standard techniques. The blocks are sectioned and stained and processed with routine H&E staining.

If a subject fails to swallow the Cytosponge, the subject will be asked to swallow again. Subjects who are willing to try again will be asked to wait 5 minutes before the Cytosponge is presented to them again. Subjects will be able to try up to three times before they are classified as "Cytosponge swallowing failure" and discontinued by the investigator.

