6.2 Statistical Methods

Aim 1: To test the hypothesis that the Cytosponge accurately quantifies esophageal eosinophil counts in patients with active EoE, the maximum eosinophil counts from the Cytosponge and endoscopic biopsy will be compared by calculating the Pearson coefficient of correlation. In addition, patients will be categorized as having an eosinophil count either above or below 15 eos/hpf (the current diagnostic threshold). Agreement between patients above and below this threshold for Cytosponge and endoscopic biopsy will be measured using the kappa statistic. If eosinophil counts are not normally distributed, non-parametric methods will be used. Separate analyses will be performed for patients with active EoE and patients undergoing treatment.

Aim 2: Summary statistics will be calculated to describe adverse events and the tolerability of the Cytosponge. The proportion of subjects who prefer the Cytosponge will be calculated.

We predict that the Cytosponge will be safe and well-tolerated in patients with EoE, and that they will prefer this minimally invasive method to endoscopy with biopsy. We also predict that the eosinophil counts obtained with Cytosponge will strongly correlate with the counts from endoscopy with biopsy in both patients with active EoE.

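### Section 6.3's only analysis set, completers with biopsy pathology, leaves swallowing failures out of the Aim 2 safety, tolerability and preference summaries

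*Combined protocol and SAP*

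**What the plan says.** Section 6.3 describes one population for the study analysis. It "will include all subjects enrolled in this study that completed the Cytosponge administration and have pathology results available from the subsequent routine care endoscopy". The sentence is not restricted to either aim.

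Section 6.2 plans two things for Aim 2. On safety and tolerability it says: "Summary statistics will be calculated to describe adverse events and the tolerability of the Cytosponge". On preference it adds one further sentence: "The proportion of subjects who prefer the Cytosponge will be calculated". Neither has its own population or denominator, and no safety or all-attempted set appears elsewhere.

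Subjects are enrolled once they are eligible and have consented (5.1.2), before the device is given. On failed swallowing, section 5.1.3 says: "Subjects will be able to try up to three times before they are classified as" a swallowing failure and discontinued. Section 4.4 adds: "Subjects unable to complete Cytosponge administration will be withdrawn from the study (discontinued by investigator"). For any withdrawal before completion, "the site should complete and submit a change of status case report form".

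On follow-up, section 4.4 says: "Withdrawn subjects will not be followed, unless they have an active adverse event (AE) at the time of withdrawal". Section 3.1 and the Study Summary, in contrast, describe safety monitoring and an acceptability survey for all patients. The Aim 2 statement in section 2 likewise refers to monitoring all enrolled patients.

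**The concern.** The requirement for a biopsy result makes sense for a paired comparison of eosinophil counts. It has no bearing on whether a subject tolerated the device. If the same set is used for Aim 2, a subject who tried up to three times and failed is enrolled, classified and withdrawn, and then counted in no summary.

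Aim 2 asks whether the device is safe and acceptable in EoE, a disease that section 1.2 says causes trouble swallowing. Inability to swallow the device is the plainest tolerability failure available. A tolerability summary restricted to those who swallowed it can lean only towards the device. Preference leans the same way if subjects who failed would not choose the sponge. No direction can be given for the adverse-event rate.

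The protocol presents its own prior evidence differently. Section 1.4.1 reports swallow success over everyone offered the device and counts the failures. Under 6.3 taken literally, this study could not report the comparable figure.

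**Working it through.** **Who falls outside the set**

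| Subject | Enrolled (5.1.2) | In the 6.3 set | Adverse events collected |
|---|---|---|---|
| Completed, pathology available | yes | yes | yes |
| Completed, no pathology | yes | no | yes |
| Swallowing failure | yes | no | yes (5.1.5, 7.2.2; reported under 7.2 if related) |

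Membership requires completion, so swallow success at the enrollment administration is n/n = 100% within the set, whatever happens in the study.

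**The protocol's own figure.** Section 1.4.1 gives 501 of 504 swallowed: 501/504 = 99.4%, stated there as 99%. The denominator is everyone offered the device.

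**Inputs**
- 3 failures in 504, primary care, earlier device (Cytosponge I) (1.4.1).
- 0 failures in 20 EoE patients, including some with strictures (1.3).
- Enrollment of up to 150, with 60 for Aim 1 (6.1).

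**Failure rates, exact (Clopper-Pearson) 95% limits**
- 3/504 = 0.60% (0.12% to 1.73%).
- 0/20: upper limit 1 − 0.025^(1/20) = 16.8%.

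**Expected failures in 150 subjects**
- At 0.595%: 150 × 0.00595 = 0.89. Chance of at least one: 1 − (1 − 0.00595)^150 = 0.59.
- At 1.73%: 150 × 0.0173 = 2.6.
- At 16.84%: 150 × 0.1684 = 25.3. This is an upper bound from 20 patients, not a forecast.

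**Effect on preference.** The documents give no preference rate. Assume that 80% of completers prefer the sponge and that no failure does. Over all who attempted, the proportion is 0.80 × (1 − f), where f is the failure rate:
- f = 0.595%: 79.5%
- f = 1.73%: 78.6%
- f = 16.84%: 66.5%

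**What reporting the proportion would show** (exact 95% limits)
- 0/60: upper limit 1 − 0.025^(1/60) = 6.0%.
- 0/150: upper limit 1 − 0.025^(1/150) = 2.4%.
- 1/150 = 0.7% (0.02% to 3.7%).

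So the study's own count would narrow the EoE upper limit from 16.8% to a few percent if failures are as rare as expected.

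**Completers without pathology.** The documents give no rate. The group should be small, because biopsies at two esophageal levels are planned as standard of care (3.1, 5.1.4).

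**The 7-day contact.** In section 5, footnote 3 to the procedures table ties the first acceptability rating to a completed administration: "The VAS should be administered immediately following completion of the Cytosponge and prior to the upper endoscopy". The second rating, the Impact of Events Scale and the preference form belong to the 7-day call (5.2.1). A withdrawn swallowing failure therefore has no acceptability measure clearly scheduled, although 3.1 speaks of all patients.

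**The case against.** The strongest reply is that 6.3 was written with Aim 1 in mind. Its pathology condition serves only the paired comparison, while sections 2, 3.1, 5.1.5 and 7.2.2 all suggest wider safety coverage. That may well be the intention, but the text does not say so. If 6.3 governs Aim 1 only, Aim 2 has no defined population, and the same sentence is needed.

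A second reply is that failures are already classified and documented, so nothing prevents their being reported. That is true, and it makes the repair easy. It does not change the stated set, which excludes them.

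A third is that the effect is tiny and that preference is not among the outcomes listed in 3.4. Both facts stand. The aim is descriptive, and sensitivity and specificity, the primary outcomes, are untouched.

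A reader might also infer that 4.4 flatly contradicts 3.1. The documents do not support that. The sentences in 3.1 and the Study Summary are overviews, whereas 4.4 is a specific withdrawal rule. The Impact of Events Scale is timed from sampling (3.1) and concerns distress from administration (5.2.2), so it largely presupposes that the device was taken. Of the acceptability questions, only the preference one plainly applies to someone who could not swallow it. What remains is uncertainty about whom the 7-day contact covers.

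**Conclusion.** The point holds as a defect in the stated analysis set. Taken literally, 6.3 removes swallowing failures, and any completers without pathology, from every Aim 2 summary. That makes swallow success 100% by construction and tilts tolerability towards the device.

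The expected size is small: about one subject in 150 at the documented 0.6%, and a preference shift of 0.5 points (1.4 points at the upper limit of 1.7%). The shift rests on the assumed 80% preference and on no failure preferring the sponge. The 0.6% comes from a different device version and setting.

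Two stronger inferences should be resisted. Safety data on failures are not lost: adverse events are assessed and recorded, and an event active at withdrawal is followed. Nor does the 16.8% limit predict a high failure rate. It shows only how little 20 patients can exclude. That pilot included patients with strictures, all of whom swallowed the device, and exclusion criterion 1 removes strictures that preclude its passage.

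The change is worth making because it corrects the denominator of one of the study's two aims at almost no cost.

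**What to change.** 1. In 6.3, limit the set of completers with pathology to the Aim 1 accuracy analyses.
2. Define the Aim 2 set as every subject with at least one swallow attempt, whatever the sponge or biopsy result.
3. In 6.2, add the swallowing-failure proportion at the enrollment administration, with an exact 95% CI, as a tolerability result. Using one record per subject keeps the binomial interval valid, since 5.3 allows samples at up to 6 time points.
4. Report preference among those who answered, with the number of swallowing failures beside it.
5. Reconcile 4.4 with 3.1 and Aim 2 by stating whether the 7-day contact covers swallowing failures.

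The cost is one or two sentences in 6.3, one each in 6.2 and 4.4, and one or two table rows. Items 1 to 4 need only counts already documented through the 5.1.3 classification and the change of status form, so they remain possible even if collection has ended. The downside is that reported tolerability may look slightly less favourable.

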7.1 Definitions

Unanticipated Problems Involving Risk to Subjects or Others

Any incident, experience, or outcome that meets all of the following criteria:

- Unexpected in nature, severity, or frequency (i.e. not described in study-related documents such as the IRB-approved protocol or consent form, the investigators brochure, etc.)
- Related or possibly related to participation in the research (i.e. possibly related means there is a reasonable possibility that the incident experience, or outcome may have been caused by the procedures involved in the research,
- Suggests that the research places subjects or others at a greater risk of harm (including physical, psychological, economic, or social harm) than was previously known or recognized.

Adverse Event

An **adverse event** (AE) is any symptom, sign, illness or experience that develops or worsens in severity during the course of the study. Intercurrent illnesses or injuries should be regarded as adverse events. Abnormal results of diagnostic procedures are considered to be adverse events if the abnormality:

- results in study withdrawal
- is associated with a serious adverse event
- is associated with clinical signs or symptoms
- leads to additional treatment or to further diagnostic tests
- is considered by the investigator to be of clinical significance

Serious Adverse Event

Adverse events are classified as serious or non-serious. A **serious adverse event** is any AE that is:

- fatal
- life-threatening
- requires or prolongs hospital stay
- results in persistent or significant disability or incapacity
- a congenital anomaly or birth defect
- an important medical event

Important medical events are those that may not be immediately life threatening, but are clearly of major clinical significance. They may jeopardize the subject, and may require intervention to prevent one of the other serious outcomes noted above. For example, drug overdose or abuse, a seizure that did not result in in-patient hospitalization, or intensive treatment of bronchospasm in an emergency department would typically be considered serious.

All adverse events that do not meet any of the criteria for serious should be regarded as **non-serious adverse events**.

Adverse Event Reporting Period

The study period during which adverse events must be reported is normally defined as the period from the initiation of any study procedures to the end of the study treatment follow-up. For this study, the study treatment follow-up is defined as 30 days following completion of the biomarker panel.

Preexisting Condition

A preexisting condition is one that is present at the start of the study. A preexisting condition should be recorded as an adverse event if the frequency, intensity, or the character of the condition worsens during the study period.

General Physical Examination Findings

At screening, any clinically significant abnormality should be recorded as a preexisting condition. At the end of the study, any new clinically significant findings/abnormalities that meet the definition of an adverse event must also be recorded and documented as an adverse event.

Post-study Adverse Event

All unresolved adverse events should be followed by the investigator until the events are resolved, the subject is lost to follow-up, or the adverse event is otherwise explained. At the last scheduled visit, the investigator should instruct each subject to report any subsequent event(s) that the subject, or the subject's personal physician, believes might reasonably be related to participation in this study. The investigator should notify the study sponsor of any death or adverse event occurring at any time after a subject has discontinued or terminated study participation that may reasonably be related to this study. The sponsor should also be notified if the investigator should become aware of the development of cancer or of a congenital anomaly in a subsequently conceived offspring of a subject that has participated in this study.

Abnormal Laboratory Values

A clinical laboratory abnormality should be documented as an adverse event if any one of the following conditions is met:

- The laboratory abnormality is not otherwise refuted by a repeat test to confirm the abnormality
- The abnormality suggests a disease and/or organ toxicity
- The abnormality is of a degree that requires active management; e.g. change of dose, discontinuation of the drug, more frequent follow-up assessments, further diagnostic investigation, etc.

Hospitalization, Prolonged Hospitalization or Surgery

Any adverse event that results in hospitalization or prolonged hospitalization should be documented and reported as a serious adverse event unless specifically instructed otherwise in this protocol. Any condition responsible for surgery should be documented as an adverse event if the condition meets the criteria for an adverse event.

Neither the condition, hospitalization, prolonged hospitalization, nor surgery are reported as an adverse event in the following circumstances:

- Hospitalization or prolonged hospitalization for diagnostic or elective surgical procedures for a preexisting condition. Surgery should **not** be reported as an outcome of an adverse event if the purpose of the surgery was elective or diagnostic and the outcome was uneventful.
- Hospitalization or prolonged hospitalization required to allow efficacy measurement for the study.
- Hospitalization or prolonged hospitalization for therapy of the target disease of the study, unless it is a worsening or increase in frequency of hospital admissions as judged by the clinical investigator.

7.2 Reportable Adverse Events

For this study, only those events that are related to participation in the study must be reported. This includes events related to:

- Cytosponge administration
- Questionnaire administration

- Any adverse event that may be **related** to participation in this study or use of the Cytosponge device (possibly, probably, or definitely related)
- Any adverse event in which the Cytosponge may **have caused or contributed** to the event.
- Any event required to be reported to the FDA and/or manufacturer per 21CFR803 including:
 - Device-related deaths;
 - Device-related serious injuries.

****Deaths due to the expected progression of disease do not need to be reported as adverse events but should be reported as an outcome for the patient.*

7.2.1 Reporting Timeline

Serious adverse events (meeting the definition of a reportable AE) or unanticipated problems involving risk to subjects or others must be reported within **24 hours** of learning of the event. To report such events, sites must complete the Reportable Event case report form. In addition to completion of the CRF, sites must also fax or email the form to [contact] or [contact]. If for any reason the form cannot be completed within 24 hours, a phone call should be made to the lead site [contact] to meet the reporting timeline. In the case of a telephone report, sites must still complete the reportable event form at the earliest possible opportunity, and no later than 72 hours following learning of the event.

All other reportable events should be reported within **15 days** of learning of the event.

7.2.2 Recording of Adverse Events

At each contact with the subject, the investigator must seek information on adverse events by specific questioning and, as appropriate, by examination. Information on all adverse events should be recorded immediately in the source document, and also in the appropriate adverse event module of the case report form (CRF). All clearly related signs, symptoms, and abnormal diagnostic procedures results should be recorded in the source document, though should be grouped under one diagnosis.

All adverse events occurring during the study period must be recorded. The clinical course of each event should be followed until resolution, stabilization, or until it has been determined that the study treatment or participation is not the cause. Serious adverse events possibly related to the study that are still ongoing at the end of the study period must be followed up to determine the final outcome. Any serious adverse event that occurs after the study period and is considered to be possibly related to the study procedures or study participation should be recorded and reported immediately.

7.2.3 Reporting Adverse Events to Lead Site

All adverse events that meet the criteria of a “reportable” adverse event as described in section 7.2 above must be reported by completing the reportable event form and entering in the study database.

All events will be reported using the National Cancer Institute’s Common Terminology Criteria for Adverse Events (CTCAE) version 4.0. A quick reference guide can be accessed from the following website: http://www.acrin.org/Portals/0/Administration/Regulatory/CTCAE_4.02_2009-09-15_QuickReference_5x7.pdf

